8.0 Criteria for Response

The International Workshop on Chronic Lymphocytic Leukemia (IWCLL) criteria will be used ¹³ (Appendix I). Responses will be assessed after 3, 6 and 12 cycles.

9.0 Evaluation of Toxicity

Adverse events are reported as per UTMDACC and Leukemia Phase 2-3 studies.

An adverse event or suspected adverse reaction is considered “serious” if, in the view of either the investigator or the sponsor, it results in any of the following outcomes:

- Death
- A life-threatening adverse drug experience – any adverse experience that places the patient, in the view of the initial reporter, at immediate risk of death from the adverse experience as it occurred. It does not include an adverse experience that, had it occurred in a more severe form, might have caused death.
- Inpatient hospitalization or prolongation of existing hospitalization
- A persistent or significant incapacity or substantial disruption of the ability to conduct normal life functions.
- A congenital anomaly/birth defect.

Important medical events that may not result in death, be life-threatening, or require hospitalization may be considered a serious adverse drug experience when, based upon appropriate medical judgment, they may jeopardize the patient or subject and may require medical or surgical intervention to prevent one of the outcomes listed in this definition. Examples of such medical events include allergic bronchospasm requiring intensive treatment in an emergency room or at home, blood dyscrasias or convulsions that do not result in inpatient hospitalization, or the development of drug dependency or drug abuse (21 CFR 312.32).

- Important medical events as defined above, may also be considered serious adverse events. Any important medical event can and should be

reported as an SAE if deemed appropriate by the Principal Investigator or the Sponsor, IND Office.

- All events occurring during the conduct of a protocol and meeting the definition of a SAE must be reported to the IRB in accordance with the timeframes and procedures outlined in “University of Texas M. D. Anderson Cancer Center Institutional Review Board Policy on Reporting Serious Adverse Events”. Unless stated otherwise in the protocol, all SAEs, expected or unexpected, must be reported to the IND Office, regardless of attribution (within 5 working days of knowledge of the event).
- All life-threatening or fatal events, that are unexpected, and related to the study drug, must have a written report submitted within 24 hours (next working day) of knowledge of the event to the Safety Project Manager in the IND Office.
- The MDACC “Internal SAE Report Form for Prompt Reporting” will be used for reporting to the IND Office.
- Serious adverse events will be captured from the time the patient signs consent until 30 days after the last dose of drug. Serious adverse events must be followed until clinical recovery is complete and laboratory tests have returned to baseline, progression of the event has stabilized, or there has been acceptable resolution of the event.
- Additionally, any serious adverse events that occur after the 30 day time period that are related to the study treatment must be reported to the IND Office. This may include the development of a secondary malignancy.

Reporting to FDA:

- Serious adverse events will be forwarded to FDA by the IND Sponsor (Safety Project Manager IND Office) according to 21 CFR 312.32.

It is the responsibility of the PI and the research team to ensure serious adverse events are reported according to the Code of Federal Regulations, Good Clinical

Practices, the protocol guidelines, the sponsor's guidelines, and Institutional Review Board policy.

- The Investigator or physician designee is responsible for verifying and providing source documentation for all adverse events and assigning the attribution for each event for all subjects enrolled on the trial
- PDMS/CORe will be used as the electronic case report form for this protocol and protocol specific data will be entered into PDMs/CORe.

Adverse Drug Reaction Reporting

AS PER UTMDACC AND LEUKEMIA PHASE II-III STUDIES (APPENDIX C AND APPENDIX D), Toxicity will be scored using CTCAE Version 4.03 for toxicity and adverse event reporting. A copy of the CTCAE Version 4.03 can be downloaded from the CTEP homepage (<http://ctep.info.nih.gov>). All appropriate treatment areas should have access to a copy of the CTCAE Version 4.03. All adverse clinical experiences whether observed by the investigator or reported by the patient, must be recorded, with details about the duration and intensity of each episode, the action taken with respect to the test drug, and the patient's outcome. The investigator must evaluate each adverse experience for its relationship to the test drug and for its seriousness.

The investigator must appraise all abnormal laboratory results for their clinical significance. If any abnormal laboratory result is considered clinically significant, the investigator must provide details about the action taken with respect to the test drug and about the patient's outcome. Abnormal lab values are only significant if they require intervention or treatment.

Events of Special Interest

Specific adverse events, or groups of adverse events, will be followed as part of standard safety monitoring activities by the Sponsor. These events will be reported to the Pharmacocyclics within 24 hours of awareness following the procedure described for SAEs and will require enhanced data collection. All Events of Special Interest will be submitted without a serious criterion selected if no other serious criterion is met.

List of Events of Special Interest

Major Hemorrhage

Defined as any hemorrhagic event, that is Grade 3 or greater in severity, or that results in one of the following: intraocular bleeding causing loss of vision, the need for a transfusion of two or more units of red cells or an equivalent amount of whole blood, hospitalization or prolongation of hospitalization.

Events meeting the definition of major hemorrhage will be captured as an event of special interest (see above).

10.0 Statistical Design

Endpoint and Design: The primary objective of this phase II study is to assess the activity of the combination of the Bruton's tyrosine kinase (Btk) inhibitor PCI-32765 and rituximab in Chronic Lymphocytic Leukemia (CLL) in high-risk CLL patients that have received prior therapy. Untreated CLL patients with high-risk disease based on the presence of a 17p deletion or *TP53* mutation will also be eligible. The primary endpoint is progression-free survival (PFS). Denote the median (T) = m_H , for the historical data (H) and m_E , for the experimental (E) trial, where T is time to progression in month. We assume that, T is distributed exponentially with median m_H , with the historical regimen and median m_E , with the new treatment. Under a Bayesian model, we will further assume that m_H , follows an inverse gamma (IG) prior with parameters (18, 85) reflecting the historical data (i.e., 20 patients with chromosome 17 abnormalities who had a median PFS of 5 months)⁶, and m_E , follows IG(2.25, 6.25) with the same mean as m_H , but with a much larger variance of 100 to reflect much greater uncertainty about PFS. Progression free survival is defined as the time interval from treatment to progressive disease or death, whichever happens earlier. Patients in complete remission (CR), partial remission (PR) or stable disease (SD) are all counted as progression-free. Due to the characteristic activity of PCI-32765, which typically induces a transient lymphocytosis during the first months of therapy⁷, which is not causing any symptoms and which is due to a re-distribution of CLL cells from the tissue compartments (bone marrow, secondary lymphatic tissues) into the peripheral blood, increases in lymphocyte counts can be expected (although in this combination with rituximab are less likely) and will not be considered as a sign of progressive disease.

Interim Analysis on PFS: We will accrue 40 patients and will monitor the PFS continuously, accrual will be terminated early if $\Pr(m_H + 2 \text{ months} < m_E \mid \text{data}) <$

0.01. The design operating characteristics based on 1000 simulations are summarized in Table 1. (Accrual of 40 patients with a rate = 3/month, 6 months additional follow-up). For example, the trial will stop early with 97.5% chance (23.3 patients in average) if the median PFS is 3 months, but stop early with 7.8% chance (38.6 patients in average) if the median PFS is 6 months.

Table1. Simulation study with maximum 40 patients:

True median PFS	Pr(stop)	Mean number of patients (25%, 75%)
3 months	0.975	23.3 (14, 33)
4 months	0.632	31.8 (24, 40)
5 months	0.240	36.6 (40, 40)
6 months	0.078	38.6 (40, 40)
7 months	0.038	39.1 (40, 40)
8 months	0.018	39.6 (40, 40)

Interim Analysis on Toxicity: The probability of toxicity (grade 3 or 4) will be monitored based on the Bayesian model (beta-binomial) by assuming a priori probability of toxicity following beta(1,1). The trial will be terminated if $\text{Prob}(\text{toxicity} > 0.25 \mid \text{data}) > 0.90$. Following this rule, the trial will be terminated if $(\# \text{ patients with toxicities})/(\# \text{ patients evaluated}) \geq 2/3, 3/6, 4/9, 5/12, 6/15, 7/18, 8/22, 9/25, 10/28, 11/31, 12/35, 13/38, \text{ or } 14/40$. The operating characteristics for toxicity are summarized in Table 2.

Table 2. Operating characteristics based on 10000 simulation study

True Prob(tox)	Pr(stop early)	Median # Pts (25%, 75%)
0.05	<0.01	40 (40, 40)
0.10	0.04	39 (40, 40)
0.15	0.11	36 (40, 40)
0.25	0.41	28 (9, 40)
0.35	0.79	17 (4, 28)
0.45	0.97	9 (3, 10)
0.55	>0.99	6 (3, 7)

Statistical Analysis: Descriptive statistical analysis will be calculated, including histograms or box-plots, proportions, range, means and standard deviations. A 95% credible interval on response rate will be estimated based on a beta-binomial distribution. Fisher's exact test and Wilcoxon rank test will be used in univariate analyses of categorical (Stage, for example) and continuous variables (Age, for example), respectively. The data analysis will be performed based on the Intent-to-treat. Survival or times to progression functions will be estimated using the Kaplan-Meier method. Toxicity will be reported by type, frequency and severity. Worst toxicity grades per patient will be tabulated for selected adverse events and laboratory measurements. The Department of Biostatistics will provide and maintain a website ("Clinical Trial Conduct") for enrolling patients on this study and evaluating the efficacy monitoring rules described above. The Clinical Trial Conduct website resides on a secure server, and access is gained through usernames and passwords provided to personnel responsible for enrolling patients and updating patient data. The website is accessed through a browser using secure socket layer (SSL) technology. Personnel responsible for enrolling patients on trials will be trained in the use of the trial website, with emphasis on the importance of timely updating of follow-up times and recording of events. The monitoring rules described below will be automatically evaluated each time patient data are updated on the trial website. If the stopping rule is met, the study statistician, research nurse, and principal investigator will each receive an email notification that the stopping boundary has been met.

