2.2 Rituximab

Rituximab is a monoclonal antibody that binds to the human CD20 antigen. Rituximab has been extensively used for the treatment of chronic lymphoproliferative disorders. As a single agent, it is able to induce a response in

up to 30% of the patients with relapsed CLL and is synergistic with chemotherapy agents and other monoclonal antibodies when used in combination¹². The rationale for combining PCI-32765 with rituximab is to potentiate the clinical efficacy of these agents without increasing their toxicity. This is based on the different mechanisms of action and the non-overlapping toxicity profile. When used as single agent, PCI-32765 typically induces a “compartment shift” of CLL cells from the tissues into the peripheral blood⁷. Clinically, this is associated with a transient surge in lymphocyte counts and lymph node shrinkage during the first weeks of treatment. Because of this lymphocytosis, the patients treated with single agent PCI-32765 often times do not achieve remissions, even though they are asymptomatic and display partial or complete responses at other disease sites. To improve the efficacy of PCI-32765, rituximab is an ideal combination partner, because this antibody is very effective in clearing the blood stream of CLL cells, but less effective at eradicating disease in lymphatic tissues and bone marrow. As such, this protocol combines two agents with complementary single agent activity in different disease sites: PCI-32765 has remarkable activity in the lymphatic tissues, and rituximab is highly effective in clearing the blood stream of CLL cells.

The side effect profile of these two agents also appears to be entirely different and non-overlapping; the toxicity of rituximab consists mainly of infusion reactions, nausea and late transient myelosuppression. PCI-32765 has a very benign side effect profile with low-grade gastrointestinal side effects, no signs of any cumulative toxicity, and no immunosuppression or myelosuppression.

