4.0 Treatment Plan

Rituximab (375 mg/m²) will be given intravenously on Day 1, Day 8 (+/- 3 days), Day 15 (+/- 3 days), and Day 22 (+/- 3 days), and then continued once every 4 weeks only on Days 1 (+/- 7 days) during cycles 2 - 6 (+/- 7 days), see Study Calendar, unless patients experience toxicities that warrant early discontinuation

of the rituximab (as determined by the treating physician). There will be no dose modifications of rituximab. PCI-32765 will be started on Day 2 of cycle 1 at a dose of 420 mg (3 x 140-mg capsules) orally once daily with 8 ounces (approximately 240 mL) of water (avoid GRAPEFRUIT JUICE due to CYP450 3A4 inhibition) and will be continued daily. There will be no dose modifications of PCI-32765. The doses and schedule of PCI-32765 is based on prior studies with this drug in patients with CLL and other B cell malignancies. At this dose, the target enzyme, Btk, is fully inhibited. The rituximab doses and schedule are considered standard for treatment of CLL patients. A subject diary will be used to aid with PCI-32765 administration compliance. Treatment duration will be 12 cycles, and it will be possible to continue beyond 12 cycles if there is a significant benefit such as an ongoing PR or CR. Response will be evaluated after three, six and twelve cycles. (Each cycle consists of 28 days, see Study Calendar).

Rituximab should be held for any Grade 4 toxicity or for any rituximab-related, clinically significant, unmanageable Grade 3 adverse events. Rituximab should be held until the adverse event returns to baseline or resolves complete. PCI 32765 should be held for any Grade 3 toxicity. PCI-32765 should be held until the adverse event returns to baseline or resolves complete. After Cycle 1, if PCI-32765 is held for > 28 days, the subject should be discontinued from the study.

Special Handling Instructions

Allopurinol at the dose of 300mg daily will be given during the first one to two weeks of treatment as standard tumor lysis prophylaxis. Unused or expired PCI-32765 will be disposed per institutional policy.

Concomitant Medication: Patients receiving Coumadin are ineligible to participate in this study. Patients who recently received Coumadin must be off this medication for at least 7 days prior to start of the study.

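### The exemption of lymphocyte-count rises from progression has no end point, although the plan justifies it only by an early, transient effect

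*Combined protocol and SAP*

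**What the plan says.** Section 10.0 makes PFS the primary endpoint: "Progression free survival is defined as the time interval from treatment to progressive disease or death, whichever happens earlier". It then exempts lymphocyte-count increases, which it says are to be expected "and will not be considered as a sign of progressive disease". The reason is that PCI-32765 "typically induces a transient lymphocytosis during the first months of therapy", described as symptom-free and caused by cells moving from tissue into blood. The same sentence adds that such rises are less likely in combination with rituximab. The background section on rituximab is narrower still: "this is associated with a transient surge in lymphocyte counts and lymph node shrinkage during the first weeks of treatment".

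Section 8.0 says "The International Workshop on Chronic Lymphocytic Leukemia (IWCLL) criteria will be used", pointing to Appendix I, and mentions no exemption. Section 4.0 says "Treatment duration will be 12 cycles, and it will be possible to continue beyond 12 cycles". Section 7.0 and the study calendar set the measurements:

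- **Blood counts:** weekly for four weeks, every four weeks to cycle 12, every 3 months in cycles 13 to 36, then every 6 months.
- **Physical examinations after the first month:** before cycles 2, 3, 4, 6, 9 and 12, then on the same 3- and 6-month schedule.
- **Marrow:** after cycles 3, 6 and 12, then every 12 cycles; not mandatory once it is consistent with complete remission.
- **CT:** after cycle 3 or 6, after cycle 12, then every 12 cycles, with a restriction to patients with measurable disease past cycle 24.

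**The concern.** The justification is limited in time and in kind, and the rule is limited in neither. A rise at cycle 10 or cycle 20, or a rise after an earlier fall, falls under the same words as the expected early surge. If it reflects resistant disease, the event is dated later, when another criterion is met.

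Later dating can only lengthen recorded PFS, in the direction that favours the regimen. It also feeds the interim rule, which stops accrual when the probability that the new median exceeds the historical median plus 2 months falls below 0.01. The historical median is 5 months in 20 patients. The documents do not say whether that figure was counted with a similar exemption. If it was not, the comparison is not like for like.

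**Working it through.** **1. Rule against reason.** The words for transience, early timing and absence of symptoms all sit in the explanation. The operative clause has no end date and does not classify a late rise or a rise after a fall. It does remove only one sign: nodes, marrow, cytopenias and death still count.

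**2. Reproducing Table 1.** Inputs from section 10.0: historical median m_H ~ IG(18, 85); new median m_E ~ IG(2.25, 6.25); 40 patients at 3 per month; 6 months' further follow-up.

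- Prior means: 85/17 = 5 and 6.25/1.25 = 5. Variance of m_E: 6.25²/(1.25² × 0.25) = 100, as stated.
- With d events and total time at risk T, m_E given the data is IG(2.25 + d, 6.25 + ln 2 × T).
- Stop if Pr(m_E > m_H + 2) < 0.01. Looks every 5 patients, with a last look at 6 months, fit the printed table.

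| True median (months) | 3 | 4 | 5 | 6 | 7 | 8 |
|---|---|---|---|---|---|---|
| Printed Pr(stop) | 0.975 | 0.632 | 0.240 | 0.078 | 0.038 | 0.018 |
| Reproduced | 0.979 | 0.633 | 0.227 | 0.073 | 0.029 | 0.013 |

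**3. Effect on the stopping rule.** Assume that a share q of progressions is blood-first and is recorded D months late. Neither q nor D is in the documents. At a true median of 4 months:

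| q | D = 2 | D = 3 | D = 6 | Observed median |
|---|---|---|---|---|
| 0 | 0.633 | 0.633 | 0.633 | 4.0 |
| 10% | 0.537 | 0.490 | 0.377 | 4.2 to 4.7 |
| 20% | 0.437 | 0.352 | 0.180 | 4.5 to 5.7 |

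Repeat runs put the starting value at about 0.65 and the lowest cell at about 0.19. A fair summary is a fall from about 0.64 to between 0.54 and 0.19.

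**4. Effect on the median under the protocol's schedule.** Assume that a blood-first progression is dated at the next marrow or CT (cycles 3, 6, 12, 24, ...) instead of at the next blood count, and that all other progressions are dated at the blood count. A cycle is 28/30.44 = 0.92 months, so cycle 12 ends at 11.04 and cycle 24 at 22.08 months. Counts then fall at 14.04, 17.04, 20.04 and so on. For an exponential median m, F(t) = 1 − 2^(−t/m).

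- *m = 18, 40% blood-first.* Without the exemption the recorded median is the first count after 18, at 20.04. F(11.04) = 0.346 and F(20.04) = 0.538. With the exemption, the share recorded by 20.04 is 0.346 + 0.6 × (0.538 − 0.346) = 0.461, below one half, so the median moves to 22.08. Shift: 22.08 − 20.04 = 2.04 months.
- *m = 12, 40%.* 0.472 + 0.6 × (0.556 − 0.472) = 0.522 by 14.04. Shift: 0.
- *m = 5.* The median falls at the end of cycle 6 (6 × 0.92 = 5.52), where marrow is due anyway. Shift: 0.

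Over medians of 5, 7, 12, 18 and 24 months and shares of 20-40%, the shift is 0 to about 2 months and the mean delay of a blood-first event is about 2.3 to 3.1 months. The shift moves in steps set by the visit grid, so 2 months is not a ceiling. Reading every 3 months as every three cycles, the 18-month case gives 22.08 − 19.32 = 2.76. At m = 15 and 40%, 0.400 + 0.6 × (0.545 − 0.400) = 0.487 by 17.04, so the median moves one visit, by 3 months.

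**5. Opposite assumption.** If the scheduled examinations reveal the progression, the mean delay is about 0.1 to 0.25 months and the shift is 0 at the five medians tested.

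**The case against.** The strongest reply is that the sentence should be read whole: it describes a known early drug effect, and a sensible assessor would not apply it to resistant disease at cycle 20. That may be the intent. But the limits were not carried into the rule, and two assessors could date the same late rise differently. Appendix I was not in the text available for this review and may contain a limit; section 10.0 does not point to it.

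Three stronger readings are tempting, and the documents do not support them.

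- **That a patient with lymphocytosis cannot progress.** The clause removes one sign. A rising count with growing nodes is still progression by the nodes, so the missing time limit matters more than the missing requirement that the rise be isolated.
- **That PFS is inflated.** The documents give neither the share of blood-first relapses nor the delay, so only the direction follows from the text. Examinations, haemoglobin and platelets may catch the progression soon afterwards.
- **That a four-weekly blood signal is lost throughout.** Counts are four-weekly only to cycle 12. A calculation that assumes monthly counts for the whole of follow-up overstates the delay.

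The reply also rightly warns that a PFS analysis with no exemption at all would score the expected early redistribution as progression and could mislead.

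**Conclusion.** The point holds as a defect in the primary endpoint definition: the exemption has no end point, and its stated reason does. If any late blood-first relapse occurs, a literal reading can only delay its date. The possible effect on median PFS runs from none, through about 2 months in the cases tested, to somewhat more at particular medians. All of it rests on an assumed 20-40% blood-first share and on which visit detects the progression.

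The effect on the futility rule is potentially larger. At a true median of 4 months, even 10% of events recorded 2 months late costs about 0.1 in stopping probability (0.633 − 0.537). This too rests on assumed shares and delays. Whether the historical comparison is affected depends on how the 5-month median was counted, which the documents do not state. The change should be made: it concerns the primary endpoint and its stopping rule, and it costs little.

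**What to change.** In the PFS definition in section 10.0:

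- Limit the exemption to what the plan describes: early lymphocytosis with no other IWCLL sign of progression, within a window that the sponsor states.
- State how a rise after that window, and a rise after an earlier fall, is classified and dated.
- Cross-reference the exemption in section 8.0 and Appendix I, so that all three say the same thing.
- State whether the historical 5-month median was counted with a comparable exemption, or that this is unknown.
- Add a sensitivity analysis of PFS that counts lymphocyte-driven progression after the early window. It should not count the expected early surge.

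The cost is a few sentences and one extra analysis of blood counts already collected. The PFS figure may come out less favourable.

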94% patients experienced an adverse event (AE), 38% patients experienced an adverse event grade 3 or greater in severity (nausea, vomiting, fatigue, diarrhea, headache, rash). The incidence of \geq grade 3 adverse events believed to be related to PCI-32765 was 17%. 14 patients experienced a serious adverse event (SAE), with “serious” defined as requirement for hospitalization. 6 SAE were considered related to study drug by the investigator. These were one case of viral lymphadenitis, one case of a subdural hematoma, one case of viral infection (follow-up reported as unrelated), one case of decreased appetite, dehydration, and asthenia, one case of sepsis, and one case of headache and dizziness (follow-up reported as unrelated viral vestibular neuritis)⁷. Two patients in this pooled analysis have died due to progressive disease.

Diarrhea, nausea, and fatigue have been the most commonly reported adverse events, with most of the reported events occurring early in treatment (cycles 1 or 2). Significant myelosuppression has been infrequent; with grade 3 or greater thrombocytopenia or neutropenia reported in less than 5% of patients. Significant hepatic or renal toxicity has been absent. In addition, with longer-term follow-up, there has been no evidence of cumulative toxicity, either overall, or related to specific events. Because of a) one event of spontaneous subdural hematoma in a patient who took ibuprofen and PCI-32765 at the time of detection of the subdural hematoma, and b) the controversial role of Btk in platelet function and aggregation, we initiated clinical and laboratory assessment of platelet function of patients treated with PCI-32765 on the ongoing Phase I/II trial. There have been no subsequent bleeding events; some patients, however, displayed petechiae or bruises. Therefore, we will implement regular clinical and laboratory assessment and exclude patients with a history of bleeding diathesis or coagulopathy, recent surgical procedure, stroke, or hemorrhage, and patients receiving Coumadin.

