The Investigator must ensure that the records and documents pertaining to the conduct of the study and the distribution of the study drug, that is copies of CRFs and source documents (original documents, data, and records (e.g., hospital records; clinical and office charts; laboratory notes; memoranda; subject's diaries or evaluation checklists; pharmacy dispensing records; recorded data from automated instruments; copies or transcriptions certified after verification as being accurate copies; microfiches; photographic negatives, microfilm, or magnetic media; x-rays; subject files; and records kept at the pharmacy, at the laboratories, and at medico-technical departments involved in the clinical study; documents regarding subject treatment and study drug accountability; original signed informed consents, etc.)) be retained by the Investigator for as long as needed to comply with national and international regulations (generally 2 years after discontinuing clinical development or after the last marketing approval). The Investigator agrees to adhere to the document/records retention procedures by signing the protocol.

Premature Discontinuation of Study

The responsible local clinical Investigator, as well as Pharmacoclics, has the right to discontinue this study at any time for reasonable medical or administrative reasons in any single center. Possible reasons for termination of the study could be but are not limited to:

1. Unsatisfactory enrollment with respect to quantity or quality.
2. Inaccurate or incomplete data collection.
3. Falsification of records.
4. Failure to adhere to the study protocol.

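### The toxicity stopping rule counts only grade 3 or 4 events, so as worded a toxicity that is only ever recorded as fatal is not counted

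*Combined protocol and SAP*

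**What the plan says.** Section 10.0, Interim Analysis on Toxicity, names the monitored event: "The probability of toxicity (grade 3 or 4) will be monitored based on the Bayesian model (beta-binomial"). The prior is beta(1,1), and the trial stops if the posterior probability that the toxicity rate exceeds 0.25 is above 0.90. The boundaries are patients with toxicities over patients evaluated, from 2/3 to 14/40. Patients evaluated is not defined.

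Section 9.0 sets the grading scale: "Toxicity will be scored using CTCAE Version 4.03 for toxicity and adverse event reporting". Elsewhere the protocol leaves the top of the scale open. Section 9.0 describes major hemorrhage with "Defined as any hemorrhagic event, that is Grade 3 or greater in severity", and Section 2.2 (PCI-32765) reports that "38% patients experienced an adverse event grade 3 or greater in severity".

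Death appears in three other places:

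- Section 9.0 requires expedited reporting: "All life-threatening or fatal events, that are unexpected, and related to the study drug, must have a written report submitted within 24 hours".
- Section 10.0 makes death a PFS event: "Progression free survival is defined as the time interval from treatment to progressive disease or death, whichever happens earlier".
- Section 11.0 gives the investigator and the drug supplier discretion over the whole study; each "has the right to discontinue this study at any time for reasonable medical or administrative reasons".

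None of these adds a fatal toxicity to the count used by the toxicity boundary.

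**The concern.** A stopping rule is applied as it is written. Section 10.0 has the monitoring rules evaluated automatically each time patient data are updated, so the coded definition decides what counts. Read literally, grade 3 or 4 leaves out the worst grade. A patient who dies of a toxicity with no earlier recorded grade 3 or 4 event would not count toward the boundary. What is at stake is the decision at the first few looks, where one event more or less settles whether the trial stops.

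**Working it through.** **Inputs (Section 10.0).** Beta(1,1) prior, limit 0.25, cut-off 0.90, at most 40 patients, 13 listed boundaries, Table 2. From Section 9.0: CTCAE 4.03. That a fatal event is grade 5 is a property of the cited scale, not printed in the protocol.

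**Formula.** With x events in n patients the posterior is Beta(1+x, 1+n−x), and

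Pr(p > 0.25 | x, n) = Σ (j = 0 to x) C(n+1, j) · 0.25^j · 0.75^(n+1−j).

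**Reproducing the plan.** All 13 listed boundaries give a posterior above 0.90. Twelve are the exact limits up to 40 patients. The exception is 11 events: 11/31 gives 0.920, but 11/32 still crosses at 0.901. The difference is one patient and is negligible. An exact recursion, looking after every patient from the third to the fortieth, gives:

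| True rate | Pr(stop), recomputed | Table 2 |
|---|---|---|
| 0.05 | 0.009 | <0.01 |
| 0.10 | 0.040 | 0.04 |
| 0.15 | 0.106 | 0.11 |
| 0.25 | 0.407 | 0.41 |
| 0.35 | 0.801 | 0.79 |
| 0.45 | 0.975 | 0.97 |
| 0.55 | 0.999 | >0.99 |

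The rule is therefore understood as the plan intends.

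**One fatal-only patient at the first boundary.** Two patients have been evaluated, one with a grade 3 or 4 event. The third patient's only severe toxicity is fatal.

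- Before the third patient, 1/2: 0.75³ + 3(0.25)(0.75²) = 0.4219 + 0.4219 = 0.844.
- As worded, patient in the denominator, 1/3: 0.75⁴ + 4(0.25)(0.75³) = 0.3164 + 0.4219 = 0.738. Continue.
- As worded, patient not regarded as evaluated, 1/2: 0.844. Continue.
- Counted as an event, 2/3: 0.3164 + 0.4219 + 6(0.25²)(0.75²) = 0.3164 + 0.4219 + 0.2109 = 0.949. Stop.

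**Later boundaries**, with one of the x patients fatal-only:

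| Boundary | Counted | As worded, in denominator | As worded, left out |
|---|---|---|---|
| 3/6 | 0.929 | 0.756 | 0.831 |
| 5/12 | 0.920 | 0.794 | 0.842 |
| 10/28 | 0.915 | 0.834 | 0.862 |
| 14/40 | 0.933 | 0.878 | 0.897 |

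Counting the patient crosses 0.90 every time. Neither reading of the present wording does.

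**Long-run size.** The documents give no fatal-only rate, so 1 to 3% is an assumption, added to a 15% rate of grade 3 or 4 events. As worded, Pr(stop) is 0.106 (true rate 0.15). With grade 5 counted it is 0.126, 0.147 and 0.171 (true rates 0.16, 0.17 and 0.18).

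**Does the PFS rule cover the gap?** Its priors are m_H ~ IG(18, 85) and m_E ~ IG(2.25, 6.25). After d events in T patient-months of total follow-up, m_E ~ IG(2.25 + d, 6.25 + T·ln 2). Accrual stops if Pr(m_H + 2 < m_E) < 0.01.

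- d = 1: 0.063, 0.079 and 0.097 at T = 1, 2 and 3. No stop.
- d = 3: 0.0046, 0.0067, 0.0093 and 0.0099 at T = 2, 3, 4 and 4.2. Stop.
- d = 3, T = 4.5: 0.0108. No stop.

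The PFS rule misses a single early death but catches a cluster of three if follow-up is still very short.

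**The case against.** The strongest reply is that the phrase is shorthand. The hold rules for PCI-32765 in Section 4.0 also speak of grade 3 or 4 events, and everyone involved would count a toxic death. Intent is probably grade 3 or higher. The hold rules do not settle the matter, because a fatal grade cannot arise when deciding whether to interrupt a drug. A likely intent is a reason to correct the phrase, not to leave it.

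Second, the problem may be rare. Section 2.2 (PCI-32765) reports two deaths in the pooled single-agent data, both from progressive disease, and describes none of the six serious events considered related as fatal. That stands, though the data are few, short in follow-up and without rituximab. Many fatal cases may also have an earlier grade 3 or 4 record and so count already.

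Third, other safeguards exist: expedited reporting, death in PFS, and discretion to discontinue. These are real. A reader might infer that toxic deaths would go unnoticed, or that the PFS rule offers no protection. The documents do not support that: three early deaths with up to about 4.2 patient-months of follow-up stop accrual under the PFS rule. What remains is that none of these safeguards puts the death into the toxicity boundary, and that the PFS rule does not respond to one early death.

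A reader might also infer that each such death necessarily lowers the posterior. That holds only if the patient is among those evaluated, a term the plan leaves undefined. If the patient is left out, the posterior does not move, and the event is still lost.

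**Conclusion.** The point holds as a defect of definition. As worded, the toxicity rule does not count a patient whose only severe toxicity is fatal, and at a boundary this turns a stop (0.949 at 2/3) into a continue (0.738 at 1/3, or 0.844 at 1/2 if the patient is left out). On average the effect is modest: Pr(stop) of 0.11 as worded against 0.13–0.17 with grade 5 counted, under an assumed 1 to 3% fatal-only rate on top of 15%.

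The conclusion rests on a fatal event being grade 5 on the cited scale and on the rule being applied literally. It does not show that the 25% limit, the boundaries or Table 2's stopping probabilities are wrong; they reproduce. It is worth fixing because the correction is small and concerns the most serious outcome the boundary is there to detect.

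**What to change.** In Section 10.0, Interim Analysis on Toxicity, define the monitored event as toxicity of grade 3 or greater (grades 3–5), and use the same definition on the trial conduct website. The prior, the 25% limit, the 13 boundaries and Table 2's stopping probabilities need no change, because they depend only on how many patients have an event. Section 9.0 already collects the data. The cost is one phrase and a slightly higher chance of stopping.

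Two side notes for the sponsor to clarify while the sentence is open; neither carries the point. The rule does not say whether all events or only drug-related events count. The 25% limit lies between the two single-agent figures in Section 2.2 (PCI-32765): 38% for all events of grade 3 or greater, and, for related events, "grade 3 adverse events believed to be related to PCI-32765 was 17" per cent. Appendices C and D, cited in Section 9.0, were not in the text available and may answer this. The plan should also say when a patient counts as evaluated, including a patient who dies.
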